
PARTICIPANT AREA	DESCRIPTION
	
not anticipated
 
Exclusion Criteria:
 
Individuals meeting any of the following criteria at baseline will be excluded from study participation:
 
 1. Prior strabismus, intraocular, or refractive surgery (including BOTOX injection) 2. Prior nonsurgical treatment for IXT (e.g., patching, vergence therapy, vision therapy/orthoptics, base-in prism, or deliberate overminus (more than 1.00 D) spectacles of >1 week duration within the past year 3. Previous amblyopia treatment other than refractive correction 4. Diplopia more than 2 times per day by parental assessment 5. Paretic or restrictive strabismus 6. Craniofacial malformations affecting the orbits 7. Ocular disorders which would reduce VA (except refractive error) 8. Severe developmental delay that would interfere with treatment or evaluation (in the opinion of the investigator). Participants with mild speech delay or reading and/or learning disabilities or ADHD are not excluded. 9. Neurological anomaly that could affect ocular motility (e.g., cerebral palsy, Down syndrome) 10. Immediate family member (child or sibling) of any investigative site personnel directly affiliated with this study. 11. Known allergy to adhesive patches. 12. Known allergy to silicone.
Sample Size	72 (36 observation, 36 full-time patching)
Phase	Phase 3
Treatment Groups	Random assignment to: 
 • Observation • Full-time patching (all waking hours, 7 days/week)
Participant Duration	3 months after randomization
Protocol Overview/Synopsis	Participants will be randomly assigned to observation or full-time patching. All parents will receive a phone call at 4 weeks to answer any questions about observation or patching treatment. Participants will be followed for 3 months.

STUDY SUMMARY FLOW CHART

- Major Eligibility Criteria**
- Children aged 3 to <9 years
 - Intermittent exotropia meeting all the following criteria:
 - Intermittent or constant XT at distance (mean distance control 2.0 or more, with at least 1 measure of 3, 4 or 5)
 - IXT or exophoria or orthophoria at near (cannot have control score of 5 on all 3 near assessments)
 - Distance deviation between 15Δ and 50Δ by PACT
 - Near deviation between 0Δ and 50Δ by PACT
 - Near deviation does not exceed distance by more than 10Δ by PACT
 - No prior strabismus, intraocular, or refractive surgery (including BOTOX injection)

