482 Participants randomized to the full-time patching group will patch full-time (all waking hours)
483 for 3 months up until the day before the 3-month primary outcome visit. Daily alternate patching
484 will be prescribed (right eye on even days, left eye on odd days). No other treatment for IXT will
485 be used, except for refractive correction.

486 **2.6 Monitoring of Adherence**

487 Site staff will activate and distribute occlusion dose monitors (ODMs) for participants
488 randomized to patching (patching adherence is not applicable to the observation group).

- 489 • Adherence with patching will be monitored throughout the study by an ODM worn on the
490 inside of the patch for participants randomized to patching.
491 • In addition, parents will be asked to record patching wear time and which eye was
492 patched on a study calendar.

493

Chapter 3: Study Follow-up

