4.5 Binocular Diplopia by Parental Report

The number and proportion of participants with binocular diplopia at 3 months with a frequency of "more than 2 times per day" over the last week at distance and near separately (by parental report) will be tabulated by treatment group and analyzed as a dichotomized outcome.

226 227

228

229

230

5 Patch Wear Time

Site staff will activate and distribute occlusion dose monitors (ODMs) for participants randomized to patching (patching adherence is not applicable to the observation group). While activated, the ODM takes a temperature reading every 20 minutes, which is used to determine whether the patch was being worn at that time.

231232

233234

235

The sensors hold 133 days of data when the time interval is set at 20 minutes. If the sensor has not been read and data downloaded for a longer period than the max storage allows (133 days), the oldest data is overwritten, so only the latest 133 days will be uploaded.

236237238

239

For days with sensor readings, the temperature threshold for considering the patch worn will be \geq 82°F (\geq 27.78 °C), versus < 82°F (27.78 °C) for not worn.⁵

For each participant in the full-time patching group, the following statistics will be reported:

240241242

• Number of participants (% of total in patching group) with ODM data.

243244245

 Distribution (median, IQR, minimum, maximum, histogram) of the percentage of days for which ODM data was obtained, including all participants randomized to full-time patching.

246247248

Percentage of days for which ODM data was obtained = (number of days for which ODM data was obtained (regardless of completeness))/(expected number of days of patching) * 100%.

249250251

Expected number of days of patching = (Date of randomization – date of 3-month visit) – 2, since expected to patch day after randomization and stop patching the day before their 3-month visit.

252253

 Number of participants (% of total in patching group) with no ODM data.

254255

Of those with data, the distribution of the number of days patching will be split into quartiles

256257

• Within each quartile, the number of participants (% of total in patching group) will be calculated.

258259

• Distribution (median, IQR, minimum, maximum, histogram) of total number of hours patched in patching group participants with ODM data

260 261 O Total number of hours patched = (Number of readings exceeding 82 degrees Fahrenheit) x 20 minutes x (1 hour / 60 minutes)

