262263264

Scatterplots, with Spearman correlation coefficients and 95% confidence intervals, will be generated to illustrate the relationship between the total number of hours patched and each outcome listed below for those with ODM data:

265266

- 267 1. Distance control score
- 268 2. Near control score
- 269 3. Distance angle of deviation
- 270 4. Near angle of deviation
- 5. Suppression Score (0=negligible, 1=mild, 2=moderate, 3=dense)
 - 6. Convergence fusional amplitudes
- 273 7. Divergence fusional amplitudes
 - 8. Symptom Survey Score
 - 9. PedEyeQ score (each domain)

275276277

272

274

The relationship between the total number of hours patched and the suppression score will be illustrated using a boxplot, rather than a scatterplot.

278279280

281

282

283

284

285

286

Patching adherence is categorized by the study coordinator as excellent, good, fair, or poor based on inspection of the patching calendar and discussion with the parent. This data will be tabulated for the 3-month visit, as will the reasons for any major deviations. Descriptive statistics and a boxplot for total number of hours patched as recorded with the ODM by level of patching adherence based on parent report will be obtained.

6 Association of Retinal Correspondence Testing to Other Outcomes

The relationship between retinal correspondence response and each of the following outcomes within each treatment group will be evaluated at 3 months:

287 288 289

290

291

293

294

295

296

- 1. Distance control score
- 2. Near control score
 - 3. Distance angle of deviation
- 292 4. Near angle of deviation
 - 5. Suppression Score (0=negligible, 1=mild, 2=moderate, 3=dense)
 - 6. Convergence fusional amplitudes
 - 7. Divergence fusional amplitudes
 - 8. Diplopia by parental assessment (dichotomized as in section 4.5)
 - 9. PedEyeQ score

Normal retinal correspondence will be defined as correspondence status marked "normal" both when aligned and tropic, while anomalous retinal correspondence will be defined as correspondence status marked "abnormal" when aligned or tropic (or both).

301 302 303

304

305

306

307

308

309

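### SAP 5 counts every sensor reading above 82°F as patch wear, with no daily maximum and no restriction to patching days, which can attenuate the exploratory wear-time correlations

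*SAP*

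**What the plan says.** SAP Section 5 describes the sensor: while activated, "the ODM takes a temperature reading every 20 minutes, which is used to determine whether the patch was being worn at that time". On classifying a reading, "the temperature threshold for considering the patch worn will be" 82°F (27.78°C) or higher. That is a lower bound only. Hours then follow from the count: "Total number of hours patched = (Number of readings exceeding 82 degrees Fahrenheit) x 20 minutes", divided by 60.

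The treatment is "Full-time patching (all waking hours, 7 days/week" (Protocol synopsis). Protocol 3.1 tells parents not to patch on the day of the visit. SAP 5 does define an expected number of patching days, "since expected to patch day after randomization and stop patching the day before their 3-month visit", but uses it only as the denominator for the percentage of days with sensor data. It does not limit which readings enter the hours.

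Total hours is the exposure in scatterplots and Spearman correlations that "illustrate the relationship between the total number of hours patched and each outcome listed below for those with ODM data". SAP 5 lists nine outcomes, and Protocol 7.8.1 places this work among the exploratory analyses. There is a second source on adherence: "In addition, parents will be asked to record patching wear time and which eye was" patched (Protocol 2.6). Under SAP 5 the coordinator rates adherence from that calendar and a talk with the parent, and sensor hours are shown by rating in a boxplot.

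**The concern.** The sensor reads round the clock, but the patch is meant to be on only while the child is awake. Even a fully adherent child therefore has many hours a day when the sensor is off the face and still recording. If it then lies somewhere above 82°F, the formula credits wear. Readings on the day of randomization and the day of the visit are also eligible, although SAP 5 does not count them as expected patching days. Neither document sets a daily maximum, a clock window, an upper temperature bound or a date limit.

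False hours can accrue only while the patch is off, so the room for error is greatest in children who wear it least. If the amount also differs between children, for example by site climate or season, recorded hours rank the children less accurately and the correlation with outcome shrinks towards zero. Protocol 1.6 lists dose-response among the unanswered questions, and Protocol 1.5 knows of no earlier study of actual wear time in this condition. The measure therefore deserves a tighter definition even in an exploratory analysis.

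**Working it through.** **1. The plan's own figures.** (82 − 32) × 5/9 = 27.78°C, as stated. One reading per 20 minutes is 24 × 60/20 = 72 readings a day. SAP 5 also states: "The sensors hold 133 days of data when the time interval is set at 20 minutes". That is 133 × 72 = 9,576 readings, so storage sets no useful limit on a 3-month total.

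**2. What the formula allows.** Assume a visit on day 91. The SAP's expected days are then 91 − 2 = 89. The formula can credit up to 24 × 89 = 2,136 h. If waking time were 12, 13 or 14 h a day (assumed; the documents give no figure), full adherence would be 1,068, 1,157 or 1,246 h.

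**3. Upper bound on inflation.** Suppose that on some days the sensor stays above 82°F for every off-patch hour. False hours = (24 − true daily hours) × such days.
- Child wearing 6 h/day: true total 6 × 89 = 534 h, with 18 false hours per warm day. For 5, 10, 20 and 30 days the recorded totals are 624, 714, 894 and 1,074 h, or 1.17, 1.34, 1.67 and 2.01 times the truth.
- Child wearing 13 h/day: true total 1,157 h, with 11 false hours per warm day. The totals are 1,212, 1,267, 1,377 and 1,487 h, or 1.05, 1.10, 1.19 and 1.29 times the truth.

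These are worst cases, since every unworn hour, nights included, is taken as warm. The number of warm days is not in the documents.

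**4. Effect on ranks.** Let p be the fraction of unworn time above 82°F. Recorded daily hours = true + p(24 − true) = (1 − p) × true + 24p. With the same p and similar follow-up in every child, this increases with true wear for any p below 1, so the ranks and Spearman's coefficient do not change. Harm requires p to differ between children.

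**5. Effect on the correlation when exposure differs.** Simulation with 200,000 children per scenario. Assumptions: 13 waking hours and 89 days; true wear a Beta(2, 1.2) fraction of waking time (median about 756 h); an outcome correlated 0.42 with true hours. Exposed children gain false hours equal to nominal hours × share of days × 89, scaled by their unworn fraction of the 24-hour day and by a random factor between 0 and 2.

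| Children exposed | Nominal h/day | Share of days | Mean false hours | Spearman, true hours | Spearman, recorded hours |
|---|---|---|---|---|---|
| none | – | – | 0 | 0.413 | 0.413 |
| 25% | 2 | 25% | 7 | 0.409 | 0.408 |
| 25% | 4 | 50% | 29 | 0.412 | 0.403 |
| 50% | 4 | 50% | 59 | 0.412 | 0.396 |
| 50% | 8 | 50% | 118 | 0.412 | 0.350 |
| 50% | 8 | 100% | 236 | 0.410 | 0.238 |

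**6. Against sampling error.** Protocol 7.3 plans 34 completers per group. For an observed 0.40 with n = 34, tanh(atanh 0.40 ± 1.96 × √(1.06/31)) gives a 95% interval of 0.06 to 0.66. The mild and moderate losses in step 5 are small beside that.

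**The case against.** The strongest reply is that nothing in the documents shows an unworn sensor reaching 82°F often enough to matter. SAP 5 cites a publication for the threshold, and Protocol 1.5 reports that the device works well for monitoring. The planned statistic uses ranks, so false wear common to all children does no harm (step 4). The reported minimum, maximum and histogram of total hours would show implausible totals. All of this stands, and it limits the point to something that can happen. The cited threshold, however, settles which temperature to use and not which readings are eligible.

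A reader might infer that the calendar is never set against the sensor. That is not so: the boxplot by coordinator-rated adherence is such a comparison. It is descriptive and does not correct the hours.

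A reader might also infer that poor adherers will look fully adherent. Step 3 does not show that. Even with 30 fully warm days, the child at 6 h/day reaches 1,074 h, still below the true 1,157 h of the child at 13 h/day.

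**Conclusion.** The gap is real: as written, the formula can credit off-face readings as wear, up to 24 h a day, including readings outside the expected patching days. It can attenuate the exploratory wear-time correlations if warm exposure is frequent, long and different between children. On the assumptions above, a coefficient near 0.41 ends between 0.41 (no visible change) and 0.24, and the loss is material only in the two heaviest scenarios. The true size cannot be obtained from the documents. It would be tempting to say that warm rooms and hot weather do distort the dose-response result, but without data on ambient exposure the documents support only that they could.

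The primary comparison (SAP 2) and the secondary outcomes (SAP 3) do not use sensor hours and are unaffected. This is a worthwhile refinement, not a flaw that threatens the trial's conclusion.

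**What to change.** In SAP 5, before the wear data are examined:
- Count only readings on expected patching days, from the day after randomization to the day before the 3-month visit. State whether that last day is included: with a visit on day 91, days 1 to 90 make 90 days, while the SAP's subtraction gives 89. The SAP formula also subtracts the dates in the order that gives a negative number.
- Pre-specify a plausible daily maximum of wear hours for analysis, for example 16 h, labelled as an assumption. Flag days above it.
- Repeat the Spearman correlations and the adherence boxplot with flagged days capped, or excluded, as a sensitivity analysis. Where days are excluded, use mean hours per retained day, because a sum would treat an excluded day as no wear.
- Use one form of the threshold. The classification rule includes 82°F and the hours formula does not.

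Do not accept sensor readings only within the wear periods on the parent's calendar. That would tie the objective measure to parent report and make the boxplot partly circular. It may also need clock times, which the protocol does not say are recorded. Keep the calendar as an independent comparison.

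The cost is a little programming on data already collected. The limitation is that a cap removes only implausible excess. A day with 6 h true and 18 h false wear is cut from 24 h to 16 h and still holds 10 false hours, and a day with 6 h true and 4 h false is not flagged at all.

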2.1 Principles to be Followed in Primary Analysis

Model assumptions for ANCOVA will be assessed, including linearity of the adjustment covariates (baseline distance control and distance PACT angle), normal distribution of the outcome, and equal variance in the treatment groups. The linearity assumption of the baseline covariates will be evaluated using scatterplots and by categorizing each of the baseline factors in the ANCOVA model to check for approximate linearity of the coefficients across the ordered categories. Each baseline covariate will be included as a continuous covariate in the model if the assumptions for linearity are met for that covariate; otherwise, the baseline covariate will be categorized.

When three measures of distance control are not performed at the outcome exam, the mean of two measurements, or failing that, a single measurement, will be used if available.

The primary analysis will follow the intention-to-treat principle, with all participants analyzed according to their randomized treatment group, with the following stipulations:

• For participants who receive non-randomized treatment between baseline and 3 months, the distance control score data from the early 3-month visit will be used for the primary outcome. Early outcome visits are not required to fall within the 3-month visit window to be included in analyses.

• Participants who miss the 3-month visit or do not complete any control testing at the 3-month visit, and who do not have an early 3-month outcome visit, will have their mean distance control score imputed using multiple imputation.

• For all participants other than above, to be included in the analysis, the 3-month visit must be completed within the analysis window defined as 46 to 137 days from randomization; otherwise, the distance control at the 3-month visit will be imputed using multiple imputation.

 The multiple imputation for missing data will be performed using Monte Carlo Markov Chain (MCMC) model. (See Section 2.3 below for further details.)

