2.2.2 Sensitivity Analysis #2: Complete Case Analysis (Excluding Imputed Control Scores)

Participants whose 3-month control score was imputed in the primary analysis will be excluded from the analysis.

2.2.3 Sensitivity Analysis #3: Complete Case Analysis (Excluding Imputed Control Scores and Early Outcome Visits)

Repeat the sensitivity analysis in section 2.2.2 excluding data from participants who completed an early outcome visit.

2.2.4 Sensitivity Analysis #4: ITT Excluding Participants with IOD 2 LogMAR Lines at Enrollment

The primary analysis will be repeated excluding participants of any age with IOD of 2 logMAR lines (8 or more letters for E-ETDRS and 2 logMAR lines for ATS-HOTV).

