2.3 Multiple Imputation of Missing Values

The multiple imputation will be performed for missing data using Monte Carlo Markov Chain (MCMC) modeling, which includes the mean distance control score at baseline and the change in mean distance control score from baseline to the 3-month (or early outcome) visit, and the distance PACT at baseline. Imputed values will be limited to the range of possible changes in mean control score (-5.0 to 3.0), using options available in the imputation software. If necessary, observed 3-month control scores may be transformed to achieve (or approximate) the normal distribution prior to imputing, and then backtransformed for analysis.

- The multiple imputation will be performed separately by treatment group to account for potential
- interaction between the treatment groups and the follow-up distance control scores. The number of
- imputations will be set to 100. Missing baseline data are not expected for distance PACT angle; however, if
- such missing data occurs, it will be imputed in the MCMC model so that participants with missing baseline
- data are included in the analysis.

3 Secondary Analyses

- All secondary analyses described below will use observed data only without imputation for missing data.
- Only data from 3-month outcome visits that occurred within the analysis window (or data from early 3-
- month outcome visits) will be included in analysis. For all secondary outcomes, the data will be tabulated,
- and means and standard deviations, or numbers with the outcome and percentages, will be calculated for
- each of the treatment groups. The false discovery rate will be controlled at 5% using the two-stage step-up
- procedure¹ to account for multiple secondary outcomes. Reported p-values and confidence intervals will
- incorporate the FDR adjustment.

120121

112

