3.3 Level of Suppression

- The proportion with each level of suppression (negligible, mild, moderate, or dense, as indicated on the
- completed follow-up worksheet) by treatment group at 3 months will be tabulated. The median and
- interquartile range for each group will be calculated and the distributions of suppression levels compared

between treatment groups at 3 months using the exact non-parametric Wilcoxon rank-sum test and twosample Hodges-Lehmann estimator.

4 Exploratory Analyses

Exploratory analyses will describe the distribution of the outcome, or change in outcome from baseline, within each treatment group and estimate treatment group differences and 95% confidence intervals (CIs), unless specified otherwise, with the purpose of identifying hypotheses for further study. All exploratory analyses will use observed data only without imputation for missing data. Only visits occurring within the analysis window will be included. As these are exploratory analyses, no adjustment for multiplicity will be made to confidence intervals and no p-values will be reported.

Continuous outcomes will be described using mean, standard deviation, and 95% CIs. Median and interquartile range (IQR) will also be reported if the outcome distribution is asymmetric. Treatment group differences and 95% CIs will be estimated using an ANCOVA model with adjustment for baseline level of the outcome. ANCOVA is relatively robust to violations of normality and homoscedasticity⁴; however, if ANCOVA model estimation of treatment group differences is of questionable validity due to violation of normality or other assumptions, actions to mitigate the violation will be undertaken. For example, for homoscedasticity violations, an ANCOVA model allowing the treatment groups to have different variances may be used and/or large outliers may be winsorized to the 5th and 95th percentiles of the overall outcome distribution (with treatment groups combined). In cases where winsorization of outliers is used, descriptive statistics for the treatment groups will be based on the outcome distribution after winsorization, and winsorized values will be noted in table/figure footnotes. Results of mitigated and original analyses will be compared for consistency, and results of both analyses reported if there are substantial differences.

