For continuous and ordered categorical outcome variables (control scores, angles of deviation, fusional amplitudes, suppression score, and PedEyeQ score), a difference in means and 95% confidence interval between participants with normal versus anomalous retinal correspondence will be estimated and illustrated using scatterplots (control scores, angles of deviation, fusional amplitudes, PedEyeQ score) or boxplot (suppression score). For categorical outcome variables (diplopia), the difference in proportions and 95% confidence interval between participants with normal versus anomalous retinal correspondence will be estimated by inverting Barnard's test using the method of Agresti and Min.² P-values will not be reported.

310 7 Subgroup Analyses of Distance Control

- The primary analysis will be repeated, stratifying by gender and race/ethnicity subgroups in accordance
- with NIH guidelines, to determine whether treatment effects within subgroups are consistent with overall
- treatment effects. These analyses will include only observed data (no imputed data). No effect modification
- is expected for these factors. A forest plot will be used to display the estimates of difference between
- treatment groups and 95% confidence intervals for each subgroup. P-values will not be reported. Subgroup
- analyses will only be performed for groups with a minimum of 10 observations per group.

317 8 Safety Analyses

- All safety analyses described below will use observed data only without any imputations for missing data.
- Only the visits that occurred within the analysis window will be included.

320321

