8.1 Deterioration

The number and proportion of participants with deterioration, as defined below, will be tabulated for each treatment group at 3 months as a safety outcome. Treatment group differences will not be reported.

324 325

327

328

329

330

- Deterioration is defined as meeting one of the following criteria at the 3-month follow-up visit:
- 326 1) Constant exotropia at least 10Δ at distance AND near by SPCT:
 - a) Constant is defined as an exotropia present throughout the examination and confirmed by cover/uncover testing performed at least 3 different times over the course of the exam (including during assessment of IXT control).
 - 2) Decrease in near stereoacuity of at least 2 levels from baseline, or to nil, measured using the Randot Preschool Stereotest.

331332333

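### SAP 8 (safety) and SAP 4 (exploratory) omit the early-outcome-visit exception in SAP 2.1 and SAP 3, so an early visit before day 46 can count for efficacy but not for safety

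*SAP*

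**What the plan says.** The SAP has four inclusion rules for follow-up visits.

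- **SAP 2.1 (primary).** As a general rule, "the 3-month visit must be completed within the analysis window defined as 46 to 137 days from randomization"; otherwise the outcome is imputed. There is an exception: "For participants who receive non-randomized treatment between baseline and 3 months, the distance control score data from the early 3-month visit will be used". The same bullet adds: "Early outcome visits are not required to fall within the 3-month visit window to be included in analyses".
- **SAP 3 (secondary).** The exception is restated in a parenthesis that goes on to name the early outcome visits: "Only data from 3-month outcome visits that occurred within the analysis window (or data from early".
- **SAP 4 (exploratory).** "Only visits occurring within the analysis window will be included". No exception is given.
- **SAP 8 (safety).** "Only the visits that occurred within the analysis window will be included". No exception is given.

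Protocol 3.5 creates the early visit. A Protocol Chair may approve it when a child has severe social difficulty or marked symptoms from IXT, and it takes place before any non-randomized treatment starts. No earliest day is set. Protocol 7.9 tabulates deterioration, acuity loss and diplopia at 3 months and gives no analysis window in days.

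**The concern.** The same examination can be valid for efficacy and invalid for safety. For a child who switches treatment after an approved early visit on, say, day 30, the control score is the primary outcome, and near control, PACT angle and suppression enter the secondary analyses. The SPCT, stereoacuity, acuity and diplopia findings from that examination do not enter SAP 8. Its PedEyeQ scores and parent-reported diplopia do not enter SAP 4.

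One of the two grounds for an early visit is significant symptoms, which may be related to the safety outcomes. The children dropped may therefore differ from those kept. The other ground, social concern, is not a safety endpoint. The tables affected hold the outcomes that the Protocol's study summary calls key safety outcomes.

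**Working it through.** **Step 1. Apply each rule to an early visit.** The window of 46 to 137 days is centred on (46 + 137)/2 = day 91.5, with half-width (137 − 46)/2 = 45.5 days. I assume that the early visit follows the full 3-month test list in Protocol 3.4 and that the child then receives non-randomized treatment.

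| Analysis | Early visit on day 45 or earlier | Early visit on days 46–137 |
|---|---|---|
| Primary (SAP 2.1) | in | in |
| Secondary (SAP 3) | in | in |
| Exploratory (SAP 4) | out | in |
| Safety (SAP 8) | out | in |

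The mismatch is confined to visits before day 46.

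**Step 2. Check for a stated reason.** SAP 8 and SAP 4 give none. Where the SAP means to remove early visits, it says so. Sensitivity Analysis #3 (SAP 2.2.3) reads: "Repeat the sensitivity analysis in section 2.2.2 excluding data from participants who completed an early outcome visit".

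**Step 3. How many visits?** The documents give no figure. As a rough gauge only, Protocol 1.2.1 reports 3-year results for the older observation cohort of an earlier trial. Assume constant rates over 3 years (1096 days) and 36 children per arm (72 randomized 1:1).

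- Treatment prescribed without motor or stereoacuity criteria: 12/183 × 45/1096 × 36 = 0.10 children per arm by day 45.
- All deterioration, using the reported 15% (the crude 25/183 is 13.7%): 0.15 × 45/1096 × 36 = 0.22 per arm.

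Neither input matches well. By definition, the 12 children had no motor or stereoacuity event. Deterioration is not itself a ground for an early visit under Protocol 3.5. Rates could also be higher here, because eligibility requires poorer control and one arm patches full-time. The figures support no more than zero or one such visit per arm as the likely outcome.

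**Step 4. Effect of one such visit.** Assume that all 36 children in the arm are seen, one of them only before day 46. Let e = 1 or 0 for an event at that visit, and let m be the number of events in the other 35. Rate with the visit minus rate without it = (m + e)/36 − m/35.

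| m | Event at the early visit (e = 1) | No event (e = 0) |
|---|---|---|
| 0 | 1/36 = 2.78% vs 0/35 = 0%; +2.78 points | 0% vs 0%; 0 |
| 3 | 4/36 = 11.11% vs 3/35 = 8.57%; +2.54 points | 3/36 = 8.33% vs 8.57%; −0.24 points |
| 5 | 6/36 = 16.67% vs 5/35 = 14.29%; +2.38 points | 5/36 = 13.89% vs 14.29%; −0.40 points |

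A missing event costs about one child in 36. A missing non-event moves the rate by a few tenths of a point.

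**The case against.** Two readings would excuse the text. First, the SAP 2.1 sentence about early visits speaks of analyses in general, and Protocol 3.5 treats the examination as the 3-month visit brought forward. Inclusion everywhere may be what was meant. This stands as evidence of intent. But the sentence sits under the primary-analysis principles, SAP 3 needed its own exception, and SAP 4 and SAP 8 say *only*. A programmer working from SAP 8 would drop the visit.

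Second, the restriction may be deliberate. Protocol 7.9.1 and SAP 8.1 tie deterioration to the 3-month visit, which Protocol 3.1 places at 3 months ± 2 weeks. The SAP 8 window is already wider than that, and an examination on day 20 reflects little exposure. This is a fair argument for keeping such visits out of tables described as 3-month results. It is not an argument for leaving their findings unreported, and the SAP does not make it.

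Other safeguards exist. Protocol 5.2 tabulates acuity and stereoacuity loss without a day limit, but names neither motor deterioration nor diplopia. Protocol 4.1 requires adverse events to be recorded, which could capture both, but recording is not tabulation. The DSMC reviews safety data at least twice a year. Control and PACT angle from the early visit still reach the secondary analyses. Protocol 5.5 encourages children who stop study treatment to remain to 3 months, so some will also have an in-window visit. That later examination may follow a change of treatment, in which case SAP 8 would tabulate it while the primary analysis uses the examination before the change.

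A reader might infer a substantial chance that a safety event will be hidden. The documents do not support this. It would require a visit before day 46, no in-window visit for that child, and a safety event at that examination. No rate is available for that combination, and the counts in the check concern the first condition at most.

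**Conclusion.** The four rules do not agree. Followed literally, they let an early visit before day 46 count for efficacy but not for safety or the exploratory outcomes. This is minor. With no such visit the effect is nil, and zero or one per arm is most likely. In the worst single-visit case, one event in 36 (2.8%) appears as 0/35. These sizes assume that all 36 children in the arm are seen and that the affected child has no in-window visit.

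Only descriptive safety rates and exploratory estimates are affected. SAP 8.1 says of deterioration: "Treatment group differences will not be reported". SAP 4 reports no p-values. Sample size, power, type I error and the primary result do not change.

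It would go too far to say that the SAP excludes all early visits from safety, since those on day 46 or later are kept. Nor do the documents show that the omission was intended or that the safety tables will be biased. They show that the grounds for an early visit make neutrality uncertain.

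**What to change.** In SAP 8 and SAP 4, add to the window sentence the parenthesis that SAP 3 already uses to admit early 3-month outcome visits. State that each child is counted once, using the visit that supplies the primary outcome, and footnote the day of each early visit.

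If the team prefers to keep these visits out of tables described as 3-month results, say so with the reason, and list their safety findings separately by arm.

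Either change is a few words in two sections plus a footnote or short listing, with no new data. The cost of the first option is that a few observations would reflect less than 3 months of exposure, which the footnote makes visible.
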